### **3.0 Introduction**

This statistical analysis plan (SAP) describes the statistical analyses to be completed by the AbbVie Statistics and Statistical Programming Departments for Study M16-127. Study M16-127 evaluates the efficacy and safety of GLE/PIB in adults with chronic hepatitis C virus (HCV) genotype (GT) 1 – 6 infection with compensated cirrhosis or without cirrhosis and with chronic renal impairment in both HCV treatment-naïve (TN) and interferon/pegylated interferon (IFN), ribavirin (RBV) and/or SOF treatment-experienced (TE) subjects.

This SAP (Version 1.0) provides details to further elaborate the statistical methods outlined in Clinical Study Protocol M16-127 incorporating Administrative Change 1 and 2 and Amendment 1 and 2 and 3 dated 30 January 2018, and describes analysis conventions to guide the statistical programming. Analyses will be performed using SAS® Version 9.4 (SAS Institute, Inc., Cary, NC) or later under the UNIX operating system.

### **4.0 Study Objectives, Design and Procedures**

#### **4.1 Objectives**

The primary objectives of this study are to assess the efficacy (by evaluating the percentage of subjects achieving SVR12) and safety of GLE/PIB in adults with chronic hepatitis C virus (HCV) genotype (GT) 1 – 6 infection with compensated cirrhosis or without cirrhosis and with chronic renal impairment in both HCV TN and TE subjects. The efficacy of GLE/PIB will be assessed based on the overall population (i.e., across treatment durations, genotypes, and cirrhosis status), and the safety of GLE/PIB will be assessed by treatment duration and cirrhosis status across genotypes.

The secondary objectives are to assess the efficacy of GLE/PIB based on the overall population (i.e., across treatment durations, genotypes, and cirrhosis status) by evaluating the following:

- The percentage of subjects with HCV on-treatment virologic failure;
- The percentage of subjects with HCV virologic relapse.

## 4.2 Design Diagram

This is a Phase 3b, open-label, non-randomized, multicenter study to evaluate the efficacy and safety of GLE/PIB for 8, 12, or 16 weeks in HCV GT1 – 6-infected subjects with chronic renal impairment, with compensated cirrhosis or without cirrhosis, who are either HCV TN or prior TE with interferon [IFN] or pegylated IFN [pegIFN] with or without RBV, or sofosbuvir [SOF] plus RBV with or without pegIFN. This study will consist of a Screening Period, a Treatment Period, and a Post-Treatment Period. A study schematic is shown below in [Figure 1](#).

[figure not shown]
The study is designed to enroll approximately 120 eligible subjects. The study enrollment will be monitored to meet the following non-mutually exclusive enrollment criteria: (1) up to approximately 40 subjects with Stage 3b CKD, (2) up to approximately 75 HCV GT1-infected subjects, (3) up to approximately 30 subjects with compensated cirrhosis.

Subjects will be enrolled into one of the following treatment arms:

- Arm A: HCV GT1, 2, 4 – 6 subjects without cirrhosis who are TN or TE and HCV GT 3 subjects without cirrhosis who are TN will be treated for 8 weeks.
- Arm B: HCV GT1, 2, 4 – 6 subjects with compensated cirrhosis who are TN or TE and HCV GT 3 subjects with compensated cirrhosis who are TN will be treated for 12 weeks.
- Arm C: All HCV GT3 subjects who are TE will be treated for 16 weeks.

Subjects with mixed HCV genotype infection should receive whichever duration is longer based on their genotypes, cirrhosis status, and treatment experience. For subjects with an indeterminate genotype, treatment duration will default to the respective GT3 duration based upon treatment-experience and cirrhosis status.

**Figure 1. Study Schematic**

### 4.3 Sample Size

It is anticipated that approximately 120 HCV GT1 – 6 infected subjects with chronic renal impairment, with compensated cirrhosis or without cirrhosis, who are either HCV TN or TE with IFN or pegIFN with or without RBV, or SOF plus RBV with or without pegIFN will be enrolled in the study. No formal hypothesis is being tested. If the observed SVR12 rate in this study is 97% among 120 HCV GT1 – 6 renally impaired subjects, then the half-width of the 2-sided 95% confidence interval (CI) using the normal approximation to the binomial distribution is 0.031 (nQuery Advisor, Version 8.0, Statistical Solutions, Ltd., Boston, MA).

## **4.4 Planned Analyses**

All analyses will be conducted by statisticians and programmers at AbbVie or designees according to the methodologies specified in this SAP.

The primary analysis will occur after all subjects have completed the Post-Treatment Week 12 Visit or prematurely discontinued from the study. For the primary analysis, data will be locked after performing appropriate data cleaning.

The end-of-study analysis will be conducted when all subjects enrolled in the study have completed the Post-Treatment Week 24 Visit or prematurely discontinued from the study. Data collected after the primary analysis will be added to a new version of the database which will be cleaned and locked at the end of the study. Results from the final analysis will be described in the clinical study report (CSR).

There is no intention of stopping the study early based on efficacy findings the primary analysis. The intention is to follow all subjects who receive study drug for 24 weeks following treatment.

## **5.0 Analysis Populations**

### **5.1 Definitions of Analysis Populations**

#### **5.1.1 Intention-to-Treat (ITT) Population**

All subjects who receive at least one dose of study drug will be included in the ITT population. Demographic, baseline characteristic, exposure, concomitant medication and medical history analyses will be performed on the ITT population overall and according to the treatment assignment, i.e., subject grouping will be based on the arm to which the subject was assigned. Efficacy analyses will be performed on the overall ITT population, combining Arms A, B and C which are the recommended duration per labelling.

### **5.1.2 Modified Intention-to-Treat (mITT) Populations**

Sensitivity analyses of SVR12 as described in Section 10.5 will be performed on the ITT population modified to exclude subjects who did not achieve SVR12 for reasons other than virologic failure (mITT-VF).

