### **Definitions for Efficacy Endpoints**

A confirmed quantifiable value during treatment is defined as any two consecutive HCV RNA measurements  $\geq$  LLOQ (or 100 IU/mL for **Breakthrough**), either both during treatment or at the final treatment measurement and the next consecutive post-treatment measurement. A confirmed quantifiable post-treatment value is defined as any two consecutive post-treatment HCV RNA measurements  $\geq$  LLOQ.

**Breakthrough** = confirmed HCV RNA  $\geq$  100 IU/mL after HCV RNA < LLOQ during the Treatment Period; or confirmed increase from nadir in HCV RNA (two consecutive HCV RNA measurements  $>$  1 log10 IU/mL above nadir) at any time point during the Treatment Period. A single breakthrough value ( $\geq$  100 IU/mL or  $>$  1 log10 above nadir) followed by lost to follow-up also will be considered a breakthrough (i.e., will not require confirmation).

**EOT failure** = HCV RNA  $\geq$  LLOQ at end of treatment with at least 6 weeks of treatment, where the HCV RNA value must be collected on or after Study Drug Day 36 and study drug duration  $\geq$  36 days.

**On-treatment virologic failure = Breakthrough or EOT failure;** if a subject meets both definitions of Breakthrough and EOT failure, he or she will be categorized as Breakthrough only.

**SVR4** = HCV RNA < LLOQ in the SVR4 window (4 weeks after the last actual dose of active study drug) without any confirmed quantifiable ( $\geq$  LLOQ) post-treatment value before or during that SVR window.

**SVR12** = HCV RNA < LLOQ in the SVR12 window (12 weeks after the last actual dose of active study drug) without any confirmed quantifiable ( $\geq$  LLOQ) post-treatment value before or during that SVR window.

**SVR24** = HCV RNA < LLOQ in the SVR24 window (24 weeks after the last actual dose of active study drug) without any confirmed quantifiable ( $\geq$  LLOQ) post-treatment value before or during that SVR window.

**Relapse12** = confirmed HCV RNA  $\geq$  LLOQ between end of treatment and 12 weeks after last actual dose of active study drug (up to and including the SVR12 window) for a subject with HCV RNA < LLOQ at Final Treatment Visit who completed treatment, excluding reinfection as described below.

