**Virologic failure for SVR12 = On-treatment virologic failure or Relapse12**

Only subjects who have at least one post-treatment HCV RNA value will be included in analyses of relapse. For the analysis of relapse, completion of treatment is defined as a study drug duration of 52 days or greater for Arm A, 77 days or greater for Arm B, and 103 days or greater for Arm C. If the last available post-treatment value is  $\geq$  LLOQ, then the subject will be considered a relapse (i.e., will not require confirmation).

HCV reinfection is defined as confirmed HCV RNA  $\geq$  LLOQ after the end of active treatment in a subject who had HCV RNA  $<$  LLOQ at Final Treatment Visit, along with the post treatment detection of a different HCV genotype, subtype, or clade compared with baseline, as determined by phylogenetic analysis of the NS3 or NS5A, and/or NS5B gene sequences. Reinfection in the case of the same HCV subtype is defined as a clade switch, as indicated by the lack of clustering between the baseline and post-treatment sequences by phylogenetic analysis. If phylogenetic analysis is not possible due to technical difficulties, HCV reinfection may be determined with a confirmed HCV genotype or subgenotype switch by the Versant HCV Genotype Inno-LiPA Assay v2.0 or Sanger assay.

Post-treatment relapse is defined as described earlier (**Relapse12**, **Relapse24**, **Relapseoverall**), and no genotype, subtype, or clade switch compared with baseline as determined by phylogenetic analysis of the NS3 or NS5A gene sequences. If phylogenetic analysis is not possible due to technical difficulties, the subject will be defined as having a post-treatment relapse unless an HCV genotype or subtype switch is confirmed by the Versant HCV Genotype Inno-LiPA Assay v2.0 or Sanger assay.

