### **Reasons for SVR12 Non-Response**

Subjects who do not achieve SVR12 (SVR12 non-responders) will be categorized as having:

1. On-treatment virologic failure (see **On-treatment virologic failure** definition);
2. HCV reinfection (see definition described earlier);
3. Relapse12;

4. Prematurely discontinued study drug with no on-treatment virologic failure (defined as any SVR12 non-responder who prematurely discontinued study drug [study drug duration < 52 days for Arm A, < 77 days for Arm B, and < 103 days for Arm C] and did not meet the **On-treatment virologic failure or reinfection** definitions);
5. Missing follow-up data in the SVR12 window (defined as any subject who completed study drug without data in the SVR12 window after applying the imputation rules and not meeting the definitions of [1], [2], [3], or [4]);
6. Other (defined as any SVR12 non-responder not meeting the definitions of [1] – [5]).

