## 10.7 Additional Efficacy Analyses

The following additional efficacy endpoints will be summarized for the ITT population:

- The percentage of subjects with HCV RNA  $< LLOQ$  at each post-baseline visit in the Treatment Period (using data as observed);
- The percentage of subjects with SVR4;
- The percentage of subjects with SVR24;
- The percentage of subjects who relapsed after achieving SVR12 (**Relapse24**).
- The percentage of subjects with virologic failure through Post-Treatment Week 12 (i.e., the SVR12 non-responders due to on-treatment virologic failure or Relapse12)

The number and percentage of subjects meeting each additional efficacy endpoint will be calculated along with a two-sided 95% CI using the Wilson's score method. Imputations for missing data will be performed as described in Section 6.3 for analysis of SVR,

virologic failure, and relapse. The first bulleted endpoint above will be presented using data as observed.

A summary of the subjects who completed treatment and relapsed (defined as **Relapseoverall**) will be prepared displaying the number of subjects relapsing overall and by SVR visit window (within the SVR4, SVR12, SVR24 windows or after SVR24 window), including the subject number and the SVR visit window corresponding to the first HCV RNA value of those indicating the occurrence of relapse. A similar summary will be prepared for subjects who prematurely discontinued treatment and relapsed after having HCV RNA < LLOQ at their Final Treatment Visit. A listing of subjects in the ITT population excluded from the relapse denominator (e.g., study drug duration < 52 days for subjects assigned to 8 weeks of treatment) will be provided, as applicable.

A listing of subject numbers and reasons for non-response to SVR12 will be prepared. A similar summary and listing will be prepared for subjects who do not achieve SVR24 (as defined in Section 10.1).

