## 10.8 Resistance Analyses

For all subjects, full length NS3/4A and NS5A from baseline samples will be sequenced by next generation sequencing (NGS). For subjects who experience virologic failure (on-treatment virologic failure or post-treatment relapse as defined in Section 10.1), full length NS3/4A and NS5A from the first sample after virologic failure with HCV RNA

$\geq 1000$  IU/mL will be sequenced by NGS. Subjects treated with study drug who do not achieve SVR12 due to reasons other than virologic failure (i.e., prematurely discontinued study drug with no on-treatment virologic failure, HCV reinfection, missing SVR12 data or other reasons as described in Section 10.1, Reasons for SVR12 Non-Response), but have a time point with HCV RNA  $\geq 1000$  IU/mL after treatment discontinuation, will have the sample at that time point sequenced.

Only samples with an HCV RNA level of  $\geq 1000$  IU/mL will undergo sequence analysis in order to allow accurate assessment of products of amplification. Therefore, if the HCV RNA level at the time of HCV virologic failure or treatment discontinuation is  $< 1000$  IU/mL, the sample closest in time after HCV virologic failure/treatment discontinuation with an HCV RNA level  $\geq 1000$  IU/mL will be used.

For each DAA target, signature amino acid positions and a key subset of amino acid positions for the respective inhibitor class are listed in Table 8. Appropriate subtype-specific prototypic reference sequence will be used for comparison with sequences from samples.

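### The mITT-VF sensitivity set drops early stoppers who rebound after treatment but keeps equally early stoppers who reach SVR12

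*SAP*

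**What the plan says.** - **The set.** Section 5.1.2 takes the ITT population and leaves out those who missed SVR12 "for reasons other than virologic failure (mITT-VF"). No responder is removed. Section 10.5 uses the set for sensitivity analyses of SVR12, and Section 10.8.1 uses it beside ITT for the baseline-variant summaries.
- **Virologic failure for SVR12.** Section 10.1 defines it as "On-treatment virologic failure or Relapse 12".
- **Relapse12.** It can occur only "for a subject with HCV RNA < LLOQ at Final Treatment Visit who completed treatment, excluding reinfection as described below". Section 10.1 adds that "completion of treatment is defined as a study drug duration of 52 days or greater for Arm A", with 77 days for Arm B and 103 for Arm C. A last available post-treatment value at or above LLOQ counts as relapse without confirmation.
- **Early stoppers who miss SVR12.** They fall in the fourth reason for non-response, "Prematurely discontinued study drug with no on-treatment virologic failure", unless they meet the on-treatment failure or reinfection definition. Section 10.8 places this category among non-responses "due to reasons other than virologic failure (i.e., prematurely discontinued study drug with no on-treatment virologic failure, HCV reinfection".
- **SVR12.** Section 10.1 times it from the last actual dose and sets no minimum duration.
- **Relapse after early stopping.** Section 10.7 recognises it: "A similar summary will be prepared for subjects who prematurely discontinued treatment and relapsed" after being below LLOQ at the Final Treatment Visit.

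**The concern.** The name and construction of mITT-VF invite the reader to take it as SVR12 with only virologic failures counted against the drug. Rebound after suppression is a virologic outcome, and Section 10.7 calls it relapse. Yet for anyone who stopped short of the duration threshold, Section 5.1.2 treats it as a reason for removal.

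The set neither excludes all early stoppers nor includes all those with a known outcome. It keeps the ones who cleared the virus and drops the ones who were suppressed and then rebounded. What is at stake is the interpretation of a supporting rate and its interval, together with the baseline-variant tables that use the same set.

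**Working it through.** **Tracing one subject through the definitions.** Take an Arm A subject with study drug duration below 52 days and HCV RNA < LLOQ at the Final Treatment Visit.

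| Later course | Section 10.1 class | In mITT-VF? |
|---|---|---|
| < LLOQ in the SVR12 window, no confirmed earlier rebound | SVR12 responder | Yes, as success |
| Post-treatment HCV RNA >= LLOQ, confirmed or as last value, not reinfection | Not Relapse12 (not completed), so premature discontinuation | No |
| No data after imputation | Premature discontinuation | No |

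The first two rows both have an observed outcome, and only the favourable one is kept.

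**What is already kept.** Breakthrough at any time on treatment counts as virologic failure whatever the duration. So does end-of-treatment failure, if the value is from Day 36 or later and duration is at least 36 days. The gap therefore concerns rebound after treatment. A subject who is quantifiable at an end of treatment before Day 36, without breakthrough, also leaves the set. That subject was not suppressed at the Final Treatment Visit and is a separate case.

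**The plan's own figure.** Section 4.3 gives a half-width of 0.031 for 97% of 120. Check: 1.96 × sqrt(0.97 × 0.03 / 120) = 0.0305, which agrees after rounding.

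**Size.** Let N be the subjects dosed, x the SVR12 responders, and r the early stoppers with post-treatment rebound. If no other non-responder is excluded:

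- as written: x / (N − r)
- with rebound counted as failure: x / N

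For r = 1 the difference is x / [N(N − 1)] = 117 / (120 × 119) = 0.0082, or 0.8 points.

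The SAP gives no rate of early stopping or rebound, so the counts below are assumptions. With N = 120 and 2 virologic failures as defined in Section 10.1:

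| r | As written | Rebound counted | Difference |
|---|---|---|---|
| 1 | 117/119 = 98.3% | 117/120 = 97.5% | 0.8 points |
| 2 | 116/118 = 98.3% (Wilson 94.0 to 99.5) | 116/120 = 96.7% (91.7 to 98.7) | 1.6 points |

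The as-written rate is the same to one decimal in both rows, although one more subject rebounded.

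**A mixed case.** Assume 116 responders and 4 non-responders: 1 virologic failure under Section 10.1, 2 early stoppers with rebound, and 1 with missing data.

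- ITT: 116/120 = 96.7%
- mITT-VF as written: 116/(120 − 3) = 116/117 = 99.1% (Wilson 95.3 to 99.8)
- mITT-VF with the 2 rebounds kept: 116/(120 − 1) = 116/119 = 97.5% (92.8 to 99.1)

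**The case against.** The strongest reply is that this is a deliberate and visible definition. Separating relapse after completed treatment from failure after incomplete treatment is a defensible convention. Section 10.8 states the classification openly. The plan also lists the subjects excluded from mITT-VF (10.5), tabulates and lists the reasons for non-response (10.3, 10.7), and summarises relapse after early stopping (10.7). No hypothesis is tested (4.3, 10.2), so no formal decision depends on the rate. All of this stands. A listing does not change the reported rate or interval, however, and the convention does not explain why early stoppers who succeed remain.

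Four stronger readings are tempting, and the SAP does not support them:

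- **The primary result is biased.** It is not. ITT counts these subjects as failures, and Section 10.5 adds a Wilson interval on ITT. Where no other non-responder is excluded, the rate with rebound counted is simply the ITT rate.
- **The fault is that the set can only raise SVR12.** Any set that removes only non-responders has x/(N − k) >= x/N, where k is the number removed. That property remains after the fix, so it is not the ground for this point.
- **All early stoppers with viral rebound are dropped.** Breakthrough, and end-of-treatment failure from Day 36, are kept.
- **The effect could be several points.** The planning rate of 97% implies 0.03 × 120 = 3.6 non-responders for all reasons. Four early stoppers with rebound plus two other failures would exceed that.

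**Conclusion.** The point holds in a limited form. Among early stoppers who are suppressed at the Final Treatment Visit and have an observed outcome, mITT-VF keeps the successes and removes the rebounds. As a measure of virologic efficacy, its rate is overstated by about 0.8 points for each such subject in 120, and by 1.6 to 1.7 points for two in the cases shown. That is below the planned half-width of 3.1 points. The direction follows from the definitions alone. The size rests on assumed counts, and if no early stopper rebounds the effect is zero. The ITT primary analysis and the Relapse12 secondary endpoint stand as written. The change is cheap and worth making, because it concerns how a supporting analysis will be read.

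**What to change.** For mITT-VF only, amend Section 5.1.2 to retain as virologic failure any SVR12 non-responder who meets all of the following, regardless of study drug duration:

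- HCV RNA < LLOQ at the Final Treatment Visit;
- post-treatment HCV RNA >= LLOQ through the SVR12 window, either confirmed or as the last available value under the existing Section 10.1 rule;
- not a reinfection.

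Use the same set for the baseline-variant summaries in Section 10.8.1. Leave Relapse12 and the Section 10.7 virologic-failure endpoint unchanged. Add a footnote that mITT-VF still excludes non-responders without such observed rebound and so can never fall below the ITT rate.

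The cost is SAP wording and one derived flag. The Section 10.7 summary of relapse after early stopping draws on the same data, but it is modelled on overall relapse and extends beyond the SVR12 window, so the flag must be cut at that window. The mITT-VF rate may be slightly lower, and its failure count may differ from virologic failure as defined in Section 10.1, which needs a second footnote.

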### **5.1.3 Safety Population**

All subjects who receive at least one dose of study drug will be included in the safety population. Safety analysis will be performed on the overall ITT population, combining Arms A, B and C.

## **6.0 Analysis Conventions**

### **6.1 Definition of Baseline, Final Treatment, and Final Post-Treatment Assessments**

#### **6.1.1 Baseline**

The baseline value refers to the last non-missing measurement collected before the first dose of study drug is received. The protocol specifies that all Day 1 assessments are to be performed prior to administering the first dose of study drug. Therefore, all Day 1 assessments for which time is not collected will be assumed to be pre-dose and the baseline value will be the last non-missing measurement collected on or before the first day of study drug administration.

All Day 1 assessments with time available must be before the time of first dose to be considered baseline, and the last non-missing measurement collected before the date and time of the first dose of study drug will be considered the baseline value. If multiple measurements that are prior to dosing are recorded on the same date and with the same time or if time is not available, then the average of these measurements will be considered as the baseline value. The same baseline value will be used for analyses of the Treatment and Post-Treatment Periods.

Safety assessments that are related to a serious adverse event that occurred on the first dose day are excluded when applying this algorithm.

